As further detailed in the section on statistical analysis, it is expected to register, during the time of observation, a difference in efficacy between EmoLED protocol group ("Group 2") and SOC protocol group ("Group 1"), in terms of "healing rate", intended as a reduction of the wound area, but also as a progress, in a broad sense, of the overall clinical situation of the lesion, in terms of pain and quality of life.

Endpoint

Primary endpoint of the study

The primary endpoint will be the outcomes comparison in terms of healing rate of lesions treated with SOC only versus lesions treated with EmoLED and SOC, on week 16th.

L.U.C.E. Study Protocol version 3.0 (24/02/2020)

Secondary endpoint

- 1) Safety of treatment
- 2) Evaluation of the healing time of the lesions treated with the standard method (Group 1) versus the lesions treated with the EmoLED Protocol (group 2);
- Evaluation of the treatment of chronic ulcers in patients undergoing standard treatment versus EmoLED treatment about life quality (QoL) in 16 weeks, through generic questionnaires as the EuroQiL-5D2 and specific questionnaires as the Wound-Qol3;
- 4) Evaluation of costs related to the treatment and control group, in both the NHS and society perspective
- 5) Evaluation of VAS scale in both groups;
- 6) Evaluation of satisfaction, complexity and helpfulness of EmoLED device, considering both the perspective of patients, and the one of doctors and health care workers involved;
- 7) Evaluation of cost-effectiveness using EmoLED for the treatment of ulcers.

Measurable parameters

The key data and lesion's pictures of each patient will be collected in the Data Collection Form, after the enrollment and the signature of the Informed Consent:

- Group 1: V1 (Visit 1 and first treatment), V2, V3, V4... until V32 (32 treatments are planned during 16 weeks, 2 per week)
- Group 2: V1 (Visit 1 and first treatment), V2, V3, V4... until V16 (16 treatments are planned during 16 weeks, 1 per week)

The parameters used to define the study result will be found through:

- Photographic images of lesions treated with EmoLED and control lesions
- Data Collection Form filled by the medical staff during the visit
- Economic/organizational impact survey
- Medical/clinical/social impact survey
- Survey on the usability of the device
- Detection of pain through VAS scale

Registration of clinical data

The data related to the evaluation of the study endpoints are acquired, for both groups, during the visits.

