80 patients will be recruited during the study; they will be randomized 1:1 to the standard treatment group and the EmoLED Protocol group. In the control group, which follows the standard treatment, patients will be visited twice a week. The EmoLED experimental Protocol group will undergo medical examination once a week; in this case, therapy will consist in the standard treatment plus EmoLED treatment.

This sample size is sufficient to compare the average rate of the injured area reduction, considering Student-T test for the comparison between independent samples, by establishing $\alpha = 0.05$, power level (1- β) = 0,8, under the assumption to have an area reduction rate after 16 weeks amounting to 50% in Group 1 (control group), a difference of 20% between Group 2 (experimental group) and Group 1, a standard deviation of averages equal to 50% of the mean values and a bilateral hypothesis.

Statistical analysis

The average rate of reduction of the injured area between the two groups will be compared using the Student-T-test, the quality of life in both groups at the baseline, after 16 weeks and the difference with the baseline will be compared using Student-T-test for independent samples.

Linear regression models will be used to value the differences between the groups to exclude any confounding factors. Due to the usually asymmetrical nature of cost distribution, the comparison of the costs related to the treatment and control group, in both the NHS and society perspective, will be made using the non-parametric Mann-Whitney U test.

Generalized linear regression models will be used to value the differences between the groups to eliminate any confounding factors.

The cost-effectiveness of both treatments in the time frame of the study (16 weeks) will be valued by calculating the incremental cost-effectiveness ratio (ICER) and expressed in terms of incremental costs for "quality adjusted years (QALY).

Extrapolations of results about the cost-effectiveness that simulate longer time-frames will be made considering decision-making models (e.g. Markov models) and eventually including the data gathered during the study with literary data and/or evidence from other studies.

Data publication policy

L.U.C.E. Study Protocol version 3.0 (24/02/2020)

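### The only within-trial cost-effectiveness measure is an ICER with no quadrant rule, and no baseline EQ-5D adjustment of its QALYs is specified

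*Combined protocol and SAP*

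**What the plan says.** Cost-effectiveness is secondary endpoint 7 (Secondary endpoint section). The Statistical analysis section says that, over the study's 16 weeks, it "will be valued by calculating the incremental cost-effectiveness ratio (ICER) and expressed in terms of incremental costs" per QALY. Longer horizons are left to modelling: "Extrapolations of results about the cost-effectiveness that simulate longer time-frames will be made considering decision-making models (e.g. Markov models".

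The documents give no net-benefit measure, threshold, dominance or quadrant rule, or interval for the cost-effectiveness result. They do not say how QALYs are formed from EQ-5D.

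Under Measurable parameters the visit load differs by design. For Group 1, "32 treatments are planned during 16 weeks, 2 per week"; for Group 2, "16 treatments are planned during 16 weeks, 1 per week".

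The Data Collection Form section has EQ-5D completed at the first visit, every 4 weeks and at the last visit. The planned quality-of-life analysis is that "the quality of life in both groups at the baseline, after 16 weeks and the difference with the baseline will be compared using Student-T-test". Two general sentences on regression follow: "Linear regression models will be used to value the differences between the groups to exclude any confounding factors" and, after the cost comparison, "Generalized linear regression models will be used to value the differences between the groups to eliminate any confounding factors". Neither names a covariate or mentions QALYs.

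**The concern.** Two gaps meet in one endpoint.

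**The ratio.** An ICER reads naturally as a price per QALY only when the new protocol costs more and gives more health. Here half the visits are removed, so savings are plausible. With savings, a better health result makes the ICER negative, which is also the sign of dearer-and-worse. A slightly worse health result makes it positive, and it then looks like an ordinary cost per QALY although it means money saved per QALY lost. Reported without its quadrant, the figure for endpoint 7 could be taken to mean the opposite of what was found.

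**The denominator.** Over 16 weeks a patient can accrue at most 0.308 QALY, so a modest utility gain yields a small QALY difference, and chance imbalance in starting EQ-5D between two arms of 40 can be as large as that difference. The baseline values needed to correct for this are already collected, but the plan does not say that they will be used for QALYs.

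**Working it through.** The plan has no figure of its own to reproduce: it states no cost, utility, QALY or ICER value. Its sample size of 80 rests on area reduction. From the documents I take 40 per arm, the 16-week horizon, EQ-5D at weeks 0, 4, 8, 12 and 16, and 16 against 32 planned visits. Utility and cost values below are assumptions.

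**1. What the ratio hides.** ICER = ΔC/ΔQ. Net monetary benefit = λΔQ − ΔC, with an illustrative λ of 30,000 per QALY.

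| ΔC | ΔQ | ICER | Net benefit |
|---|---|---|---|
| −400 | +0.01 | −40,000 | +700 |
| +400 | −0.01 | −40,000 | −700 |
| −400 | +0.002 | −200,000 | +460 |
| −800 | +0.002 | −400,000 | +860 |
| −400 | −0.01 | +40,000 | +100 |
| +400 | +0.01 | +40,000 | −100 |

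Rows 1 and 2 share an ICER but have opposite meanings; so do rows 5 and 6 at this threshold. Rows 1, 3 and 4 are all cheaper-and-better, yet their ICERs (−40,000, −200,000, −400,000) do not follow the order of their value (700, 460, 860). This part needs no utility assumption.

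**2. Precision of the QALY difference.** QALY = Σwₖ·EQ-5Dₖ with w = (4/52)×(0.5, 1, 1, 1, 0.5). So Σw = 16/52 = 0.3077, (Σw)² = 0.09467 and Σw² = 0.02071.

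Assume utility SD σ = 0.25, equal correlation ρ between readings, and a group difference rising linearly to 0.05 at week 16.

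- True gain: 0.05 × ½ × 16/52 = 0.0077 QALY.
- Unadjusted variance: σ²[(1−ρ)Σw² + ρ(Σw)²]. At ρ = 0.6: 0.0625 × (0.00828 + 0.05680) = 0.00407. SE = √(2×0.00407/40) = 0.0143.
- Slope of QALY on baseline: b = w₀ + ρ(Σw − w₀) = 0.0385 + 0.6×0.2692 = 0.200.
- Adjusted variance: 0.00407 − b²σ² = 0.00407 − 0.00250 = 0.00157. SE = 0.0089, which is 38% smaller.
- Chance of a wrong sign: Φ(−0.0077/SE), about 29% unadjusted and 19% adjusted.
- Baseline imbalance of one SE: 0.25×√(2/40) = 0.056 in EQ-5D. Times 0.200, this shifts the unadjusted difference by 0.011 QALY, more than the true gain.

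The percentage reduction in SE does not depend on σ, only on ρ:

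| ρ | SE unadjusted | SE adjusted | Reduction | Wrong sign, unadjusted → adjusted |
|---|---|---|---|---|
| 0.3 | 0.0116 | 0.0095 | 18% | 25% → 21% |
| 0.6 | 0.0143 | 0.0089 | 38% | 29% → 19% |
| 0.8 | 0.0158 | 0.0069 | 56% | 31% → 13% |

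Over a wider set of assumptions (SD 0.15–0.30, ρ 0.5–0.7), the chance of a wrong sign is:

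| Week-16 gain | Unadjusted | Adjusted |
|---|---|---|
| 0.02 | 35–43% | 26–39% |
| 0.05 | 17–34% | 6–25% |
| 0.10 | 3–20% | 0.1–8% |

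**3. Both parts together.** Take σ = 0.25, ρ = 0.6, gain 0.05, a mean saving of 400 and a cost SD of 600. In simulation, 70% of unadjusted results are cheaper-and-better and 29% cheaper-and-worse. The central 95% of ICERs runs from about −396,000 to +379,000. Net benefit at 30,000 runs from −252 to 1,507: one readable range, but still wide and including zero.

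**The case against.** The strongest reply is that nobody can compute an ICER without first having the cost and QALY differences, whose signs name the quadrant. A competent analyst would report cheaper-and-better as dominance. Costs and quality of life are also compared separately, and longer horizons are to be modelled, so the ratio would not stand alone. This largely stands. A reader might infer that the ICER cannot be interpreted at all in this trial; the documents do not support that. What remains is that the plan does not require the quadrant or either mean difference to be shown. The Mann-Whitney test on costs does not estimate the mean difference that the ratio uses.

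Second, a reader might infer that QALYs will go unadjusted. The documents are silent rather than contrary: the regression sentences do not exclude baseline EQ-5D, and change from baseline is analysed for quality-of-life scores. The accurate statement is that no baseline adjustment of QALYs is specified.

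Third, the wrong-sign percentages measure sampling error in the QALY difference, not a defect of the ratio. The QALY term in net benefit would have the wrong sign just as often. This objection is correct. Net benefit repairs ordering and interpretation; adjustment reduces the error and intervals display it.

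Fourth, neither a saving nor a very small QALY difference is established. Total costs also include hospitalisation, complications, informal care and lost productivity (Data Collection Form section), no unit costs or utilities are given, and the protocol expects a quality-of-life difference. Both are plausible conditions here, not facts.

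**Conclusion.** The concern holds as a gap in specification. The sole within-trial cost-effectiveness measure is a ratio whose sign and size are ambiguous unless the quadrant is named, in a design where savings are plausible. That ambiguity is algebraic and rests on no assumed utilities.

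The gain from adjusting QALYs for baseline EQ-5D does rest on assumptions. The SE falls by 18% to 56% for within-patient correlations of 0.3 to 0.8. At SD 0.25 and a linear gain to 0.05, the wrong-sign chance falls from 25–31% to 13–21%, with little benefit at the low end of correlation (25% to 21%).

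The change is worth making because it is nearly free. It concerns one secondary endpoint and does not touch the primary analysis.

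**What to change.** In the Statistical analysis section:

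1. Define QALYs as the area under the EQ-5D curve over the scheduled assessments to week 16, and estimate the group difference by regression on group and baseline EQ-5D.
2. Report the mean cost difference and the mean QALY difference, each with an interval.
3. Report incremental net monetary benefit with its interval over a stated range of thresholds.
4. Give the ICER only with its quadrant named, and state dominance as such.

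This costs a few lines of analysis text and needs no new data, visits or patients. The one decision required is that the sponsor name the threshold range, preferably before results are seen so that it cannot be chosen to suit them.
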